### SECTION III: STUDY PROTOCOL

15. **Study Abstract:** Provide a brief, non-technical summary of the study, including study purpose and methods.

The purpose of this study is to quantify the impact of a formalized pain management education program on the outcome and experience of patients undergoing outpatient, upper extremity, orthopedic surgery. Outcome measures include the validated Quality of Recovery-15 patient survey and PROMIS survey (selected short forms evaluating pain and medication side effects), as well as measures of patient behavior (amount of pain medication used, number of calls/visits to a medical provider for pain-related concerns), pain levels (1-10 scale), reported side effects, and patient knowledge as measured on a follow-up questionnaire. It is the premise of this study that patient education regarding perioperative pain management could benefit patients in several ways:

- 1) empowering patients to make informed decisions regarding the pain medications and modalities they choose,
- 2) reducing the incidence and severity of pain medication related side effects or complications,
- 3) improving post-operative pain control,
- 4) improving patient satisfaction, and
- 5) reducing the use of narcotic.

Four hundred (400) adult patients undergoing elective outpatient, upper extremity, orthopedic surgeries will be recruited by the surgeon-investigators. Patients will be randomized to view one of two educational programs: 1) a 2-video series regarding post-operative pain management or 2) a video regarding wound care and activity. Randomization will be stratified based on initial narcotic prescription size, which has been shown to influence narcotic use, and baseline pain medication use.

These patients will be encouraged to review the video online in the week before surgery. An intake enrollment form will be completed by an investigator using demographic information available in the chart.

Participants in both arms will complete their Patient Education Study Diary daily, for 7 days following their surgery. There are two versions of this diary: the Wound Education Version asks patients to report daily pain medication use. The Pain Education Version does not include this section as patients in the pain management arm of the study record this information in their Recovery Diary.

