17. **Objectives:** State the research hypothesis or the question that the research will answer. List the research objectives and expected outcomes. **A primary outcome or objective must be identified.** After the statement of the primary objective, secondary objectives may be listed. Objectives should be simple and specific.

Hypothesis: Patient experience and outcome after outpatient upper extremity orthopedic surgery can be improved by a formalized education program (video and handout) regarding post-operative pain management.

Primary outcome:

1. QoR-15 scores (post-operative day "POD" 2),
  - a. 15-question validated outcome measurement tool used in the setting of outpatient surgery which takes about 2.5 minutes to complete and includes pain as one of its outcome domains

Secondary Outcomes:

2. PROMIS short forms administered on POD 3 – (GI belly pain 5a, GI nausea and vomiting 4a, Pain Intensity 3a, Pain Interference 4a, Sleep Disturbance 4a, Cognitive Function 4a)
3. number of narcotic pills used – 7 days,
4. daily pain level (by 0-10 rating scale) – 7 days,
5. patient-reported satisfaction and feeling of control (4 point rating scale)
6. number of pain-related calls/visits to a healthcare provider
7. use of non-narcotic adjunct pain relief medication and modalities
8. incidence of high risk activities (combining narcotics with muscle relaxants/sedatives/alcohol, etc.; combining prn NSAIDs with regularly dosed prescription NSAIDs, exceeding daily recommended doses)
9. incidence of side effects and adverse events,
10. demonstrated patient knowledge as measured by score on the follow-up quiz, and
11. prevalence of chronic opioid use.

Positive improvements in some or all of these measurements are expected with this patient education intervention. The Quality of Recovery-15 survey is a 15-question validated outcome measurement tool used in the setting of outpatient surgery which takes about 2.5 minutes to complete and includes pain as one of its outcome domains

18. **Study Design:** Give a description of the research design including use of placebo, randomization and an explanation of what is experimental. Include type of study: descriptive, retrospective, cross-sectional, longitudinal, prospective observational, pilot, experimental (controlled or non-controlled) or pilot.

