#### Inclusion Criteria

1. Adult (age 18 or older) patients planning elective outpatient orthopedic surgery procedures by a Carilion Clinic hand surgeon will be eligible for the study.

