#### Exclusion criteria will include:

1. Patients unable or unwilling to provide informed consent
2. Patients unable to unwilling to participate in the trial (poor English language skills, blindness, cognitively disadvantaged, poor literacy skills, other barriers to participation)
3. Patients who are or suspect they may be pregnant.
4. Patients for whom the medical provider, in his professional judgment, does not feel that the study protocol would be appropriate. (to be tracked)

Inclusion and exclusion criteria were selected by the PI with the intention to make the study population as inclusive as possible to represent since the goal of the videos is to have them available

for general patient viewing. Pediatric patients and pregnant patients are excluded as these represent populations with special ethical and medical considerations (such as drug dosing, medication effect on the fetus) which are not addressed in this study. Also, the educational program is designed for adult learners.

20. **Methodology:** List all activities or procedures that will be performed (pre-treatment tests and medications, tests and medications used during therapy, diagnostic tests, x-rays, lab tests, questionnaires and other forms, interviews, chart reviews etc.) Describe how, when and where research activities will be administered and analyzed. **Distinguish any standard processes from those that are research.** Please describe activities/procedures in a step-by-step chronological order. State the length of time subjects will be in the study and the expected amount of time required for each study visit or activity.

1. Recruitment – 10 minutes

A desk-top sign advertising the study will be displayed in patient rooms used by the Hand Section providers for patient visits.

All patients who are consented or scheduled for surgery during a clinic visit with a Hand Section provider at the ION building (when a designated enrollment investigator is present/available) will be considered for the study. These patients will be referred to the designated enrollment investigator, who will present the participation opportunity to the patient after the conclusion of the visit with the provider. The designated enrollment investigator may be a study coordinator, medical student, or other investigator, but will not be the treating physician. Study coordinators will be utilized in this role whenever possible, although scheduling and budget restraints will make mixed coverage necessary.

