The surgeon will inform the designated enrollment investigator (verbally) of the anticipated prescription class for use in randomization. The designated enrollment investigator will send the surgeon a staff message in EPIC to document that number for reference on the day of surgery.

Patients who agree to participate in the study will sign the consent form. The designated enrollment investigator will keep track of all patients who are consented for surgery but do not enroll in the study, collecting only the number of such patients and their reason for not entering the study (patient declines or which eligibility criterion is not met). No identifying data or other demographic data will be collected from patients who do not consent to enter the study. This information will be recorded in REDCap.

2. Randomization - < 1 minute

They will then be randomized to a study group using a REDCap stratified randomization protocol.

Randomization will be stratified by anticipated post-operative prescription (none, tramadol, 10 narcotic pills, 20 narcotic pills, 30 narcotic pills, >30 narcotic pills). Other factors that will be controlled for through randomization include:

1)

The surgeon and other treating providers will be blinded as to the randomization of the patient. In some cases, the patient may initiate a discussion with the surgeon which necessarily reveals the randomization – this is necessary to avoid interference with physician-patient communication (avoiding negatively impacting patient care) and will be considered acceptable for this study.

3. Data collection – enrollment phase – 10 minutes

An enrollment form is completed by the designated enrollment investigator based on patient interview and/or chart review at the time of enrollment.

At the pre-operative visit prior to video viewing, patients will complete, using REDCap online with the assistance of an investigator, the following:

- I. Quality of Recovery 15 (2.5 minutes)
- II. PROMIS short forms in the following domains: (approximately 6 minutes)
  - a. Physical Health – Gastrointestinal - Belly Pain 5a
  - b. Physical Health – Gastrointestinal – Nausea and Vomiting 4a
  - c. Mental Health – Cognitive Function 4a
  - d. Sleep Disturbance 4a
  - e. Pain Intensity 3a
  - f. Pain Interference 4a
- 4. Educational Intervention (experimental): (6-12 minute video, depending on randomization)
  - 1) Pain Management Education (Intervention)

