Participants in both arms will complete a Patient Education Study Diary daily for 7 days following their surgery. Patients in the control group (wound care) will also record all pain medications used each day along with any side effects of the medications. Participants in the intervention (pain management) group will record their pain medication use in the additional Recovery Medication Diary provided.

Patients will receive a phone call from either an investigator or the study coordinator on Day 1-3 and Day 5-7 to remind them to complete their diaries and to answer any questions the patient may have (see attached script).

Patients will return their diaries at their first post-operative visit. If they do not bring the diaries to the post-operative visit, they will be given a self-addressed, stamped envelope to facilitate return. Patients will be contacted by phone (with permission) <10 days and 14-21 days following surgery and again 21-28 days after surgery if they have not returned their study materials as a reminder.

The Follow-up Questionnaire will be completed at the 1st post-operative visit, or by phone within 7-10 days of that appointment. The patient will be contacted again by phone and/or mail 1 year after surgery

(12-14 months) using the contact information available in EPIC to determine the self-reported prevalence of chronic pain and pain medication use:

1. Do you have pain on a daily or weekly basis?
2. In the past year, have you taken prescription opioid (or narcotic) pain medication most days or most weeks?
3. In the past year, have you used pain medications (prescription or over the counter) most days or most weeks? (list medications used on a daily or weekly basis for pain)

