## 7. Data Storage, Data Entry and Statistical Analysis

Paper copies of study materials containing confidential patient information will be stored in locked boxes in the nursing station and in locked drawers in locked areas of the clinic/physician offices. Electronic copies of study materials/collection tools containing patient identifiers/confidential information will be stored on the Carilion S drive or on REDCAP as appropriate. All paper and electronic copies will be retained for 7 years and destroyed according to Carilion accepted research procedure.

A working binder will be maintained for logistical purposes to track and coordinate enrollment, follow-up phone calls and visits, and collection of study materials. The binder will list subject number, name, phone number, dates of surgery and visits, and have columns to track progress through the study protocol. It will be maintained in a locked drawer in a locked office.

Data Entry will be carried out by the investigators.

Statistical analysis will be carried out with assistance of a Carilion Clinic biostatistician. Statistical analysis will include description of the study population and comparison of study groups based on demographic variables. This will include age, surgical site (hand, wrist, forearm/elbow, humerus/shoulder), and type of anesthesia (general vs. local) as these have been shown to affect post-operative narcotic use. Analysis regarding the effect of age, gender, and surgery and medication related variables on the outcome measures will also be carried out. Primary and secondary outcome measures will be

- a. QoR-15 scores (primary outcome),
- b. PROMIS scores,
- c. number of narcotic pills used,
- d. daily pain level (by 0-10 rating scale),

- e. patient-reported satisfaction and feeling of control (4 point rating scale),
- f. number of pain-related calls/visits to a healthcare provider
- g. use of non-narcotic adjunct pain relief medications and modalities,
- h. incidence of high risk activities (combining narcotics with muscle relaxants/sedatives/alcohol, etc.; combining prn NSAIDs with regularly dosed prescription NSAIDs, exceeding daily recommended doses)
- i. incidence of side effects and adverse events,
- j. demonstrated patient knowledge as measured by score on the follow-up quiz, and
- k. prevalence of chronic pain, long term narcotic and non-narcotic pain medication use. .

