**Patient Demographic Data:**

Name

EMPI

CSN

MRN

Contact phone number

Age

Gender

Pre-existing pain medication use (opioids, acetaminophen, NSAIDS, Lyrica, Neurontin)

Patient race, ethnicity, education level

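### The 1-year opioid outcome pools continuing prior users with new chronic users; keep it, but compare arms by baseline opioid use and report the two groups separately

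*Protocol*

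**What the plan says.** **Outcome.** Item 17 (Objectives) lists the 1-year opioid outcome as "prevalence of chronic opioid use". Item 20, subsection 7 (Data Storage, Data Entry and Statistical Analysis), words it as "prevalence of chronic pain, long term narcotic and non-narcotic pain medication use". Neither speaks of new use or separates patients by opioid use before surgery.

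**Question asked.** Item 20, subsection 6 (Data Collection), puts this to each patient at 12 to 14 months: "In the past year, have you taken prescription opioid (or narcotic) pain medication most days or most weeks". It does not ask when the use began or for what condition.

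**Who is eligible.** The single inclusion criterion is "Adult (age 18 or older) patients planning elective outpatient orthopedic surgery procedures by a Carilion Clinic hand surgeon will be eligible for the study". None of the four exclusions concerns opioid use, although one leaves room for the provider's judgment. The stated aim was to "make the study population as inclusive as possible".

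**What is known at baseline.** Item 21 (Patient Demographic Data) records "Pre-existing pain medication use (opioids, acetaminophen, NSAIDS, Lyrica, Neurontin".

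**Use of that variable.** The study abstract (item 15) says randomisation is stratified on initial prescription size, "which has been shown to influence narcotic use, and baseline pain medication use". Item 20, subsection 2 (Randomization), names only the anticipated prescription. It then says "Other factors that will be controlled for through randomization include", and the list that follows is empty in the text available. Item 20 also promises a general analysis of how demographic, surgical and medication variables affect the outcomes, without naming prior opioid use.

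**The concern.** A yes at 1 year can mean two different things: a patient on opioids before surgery is still on them, or a patient who was not has become a regular user. Education about post-operative pain might affect both, but probably not to the same degree.

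If continuing users supply many of the cases, they add similar numbers to each arm and move the risk ratio towards 1. A null result could then mean no effect on new use, no effect on continuation, or an effect on one masked by the size of the other group. The variable needed to tell these apart is collected, yet neither the outcome nor the stated comparison of arms uses it.

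**Working it through.** **The plan's own figure.** The only sample-size calculation is for the QoR-15. With a difference of 8, SD 25, two-sided alpha 0.05 and power 0.80, n = 2 × (1.960 + 0.842)² × 25² / 8² = 153.3, so 154 per group. Allowing 20% attrition, 154 / 0.80 = 192.5, so 193, rounded up to 200. This agrees with the protocol. No figure is given for the 1-year opioid outcome.

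**Inputs for the check (assumptions, not in the documents).**
- b, share of patients using opioids before surgery: 5–20%.
- s, share of those still using at 1 year: 60–80%.
- q, new chronic use in control patients not using at baseline: 4%, halved to 2% by the programme.
- 160 analysed per group (200 × 0.80). This borrows the attrition allowance planned around a day-2 primary outcome; loss at 12–14 months could be larger.

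**Formulas.** Control prevalence = b·s + (1 − b)·q. Prior users' share of control cases = b·s / [b·s + (1 − b)·q]. The first set of results takes s as equal in both arms.

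**Central case, b = 10%, s = 80%.** Control: 0.10 × 0.80 + 0.90 × 0.04 = 11.6%. Programme: 0.10 × 0.80 + 0.90 × 0.02 = 9.8%. Prior users' share of control cases: 0.080 / 0.116 = 69%. Risk ratio: 0.098 / 0.116 = 0.84, against 0.50 in non-users. Absolute difference: 1.8 points, against 2.0 in non-users.

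**Range.**

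| b | s | Control | Programme | Risk ratio | Prior users' share of control cases |
|---|---|---|---|---|---|
| 5% | 60% | 6.8% | 4.9% | 0.72 | 44% |
| 5% | 80% | 7.8% | 5.9% | 0.76 | 51% |
| 10% | 60% | 9.6% | 7.8% | 0.81 | 63% |
| 10% | 80% | 11.6% | 9.8% | 0.84 | 69% |
| 20% | 60% | 15.2% | 13.6% | 0.89 | 79% |
| 20% | 80% | 19.2% | 17.6% | 0.92 | 83% |

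Prior users pass half of control cases once b exceeds q / (s + q). With s = 80% that is 0.04 / 0.84 = 4.8% for q = 4%, and 0.10 / 0.90 = 11.1% for q = 10%. The share can be smaller: with b = 5%, s = 80% and q = 10% it is 0.040 / 0.135 = 30%.

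**Power, and what baseline use adds.** Take b = 10%, control s = 80%, q halved from 4% to 2%, two-sided 0.05, 160 per group. The unadjusted and non-user columns use the arcsine formula. The stratified column is from simulation of a comparison stratified by baseline use; repeat runs differed by about a point. The non-user column uses 160 × 0.90 = 144 per group.

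| s in programme arm | All patients, unadjusted | All patients, stratified | Non-users only |
|---|---|---|---|
| 80% (no effect in prior users) | 8% | 11–12% | 17% |
| 70% | 13% | 21–22% | 17% |
| 60% | 21% | 34–35% | 17% |

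Stratifying by baseline use raised power in every row. Restricting to non-users gives the most power only if the programme does nothing for prior users, and then on few events: about 144 × 0.04 = 5.8 against 144 × 0.02 = 2.9.

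**The case against.** **All-patient prevalence is a legitimate outcome.** The videos are meant for general viewing, and the hypothesis concerns all enrolled patients. The pain video covers opioid risks and non-opioid options, so prior users may also benefit. This stands. A reader might infer that the outcome should become new persistent use among non-users, but nowhere does the protocol make new use the question, and the last two rows of the power table show that this restriction can cost power.

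**The absolute effect is barely changed.** A reader might infer that prior users would hide any effect. In the central case the difference is 1.8 points against 2.0. What suffers is the risk ratio, the precision and the reading of a null.

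**Randomisation already handles it.** It does prevent bias between arms, and no claim of bias is supported. If randomisation is stratified on baseline medication, as the abstract says, balance is tighter still. But balance does not remove the continuing users from the cases or separate the two kinds of yes.

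**Covariates belong in the SAP.** In part. An SAP may exist and may name the covariate. The outcome itself, however, is fixed here as a pooled prevalence, and the general sentence on medication variables neither adjusts the comparison of arms nor splits the result.

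**The outcome is secondary and underpowered anyway.** True, and this limits the importance of the point.

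A reader might also extend the argument to the 1-year pain question, using baseline PROMIS pain as the adjustment. Nothing worked out here supports that, and it is not part of this point.

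**Conclusion.** The point holds as a small, free improvement. The outcome combines continued and new opioid use, prior users are eligible, and the recorded baseline variable is not tied to this outcome.

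The consequence is dilution and difficulty of interpretation. With 5–20% prior users, 60–80% continuing and 4% new use, prior users are 44–83% of control cases, and a halving of new use appears as a risk ratio of 0.72–0.92 if continuation is the same in both arms. All of these inputs are assumptions, and a higher rate of new use shrinks the share, as in the 30% example. Unadjusted all-patient power is 8–21% in the scenarios tabulated. Stratifying by baseline use raises it to roughly 11–35%, which still leaves the outcome underpowered. The gain is a somewhat more precise comparison and a result that can be read.

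**What to change.** - Keep all-patient prevalence at 1 year as the outcome.
- State that the arms are compared with adjustment for, or stratification by, pre-existing opioid use.
- Prespecify two descriptive results beside it: new persistent use in patients not using opioids at baseline, and continued use in those who were.
- Define baseline use. Item 21 lists the drugs without frequency or duration, so say what counts as a prior user.
- Reconcile the abstract and the Randomization subsection on whether baseline pain medication use is a stratification factor.

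The cost is analysis wording plus that definition, with no extra patients or visits. If the definition is to rest on frequency or duration and the enrolment form does not already capture it, one more item on that form would be needed. The wording should be settled before the 1-year data are examined.

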#### Inclusion Criteria

1. Adult (age 18 or older) patients planning elective outpatient orthopedic surgery procedures by a Carilion Clinic hand surgeon will be eligible for the study.

#### Exclusion criteria will include:

1. Patients unable or unwilling to provide informed consent
2. Patients unable to unwilling to participate in the trial (poor English language skills, blindness, cognitively disadvantaged, poor literacy skills, other barriers to participation)
3. Patients who are or suspect they may be pregnant.
4. Patients for whom the medical provider, in his professional judgment, does not feel that the study protocol would be appropriate. (to be tracked)

Inclusion and exclusion criteria were selected by the PI with the intention to make the study population as inclusive as possible to represent since the goal of the videos is to have them available

for general patient viewing. Pediatric patients and pregnant patients are excluded as these represent populations with special ethical and medical considerations (such as drug dosing, medication effect on the fetus) which are not addressed in this study. Also, the educational program is designed for adult learners.

20. **Methodology:** List all activities or procedures that will be performed (pre-treatment tests and medications, tests and medications used during therapy, diagnostic tests, x-rays, lab tests, questionnaires and other forms, interviews, chart reviews etc.) Describe how, when and where research activities will be administered and analyzed. **Distinguish any standard processes from those that are research.** Please describe activities/procedures in a step-by-step chronological order. State the length of time subjects will be in the study and the expected amount of time required for each study visit or activity.

1. Recruitment – 10 minutes

A desk-top sign advertising the study will be displayed in patient rooms used by the Hand Section providers for patient visits.

All patients who are consented or scheduled for surgery during a clinic visit with a Hand Section provider at the ION building (when a designated enrollment investigator is present/available) will be considered for the study. These patients will be referred to the designated enrollment investigator, who will present the participation opportunity to the patient after the conclusion of the visit with the provider. The designated enrollment investigator may be a study coordinator, medical student, or other investigator, but will not be the treating physician. Study coordinators will be utilized in this role whenever possible, although scheduling and budget restraints will make mixed coverage necessary.

The surgeon will inform the designated enrollment investigator (verbally) of the anticipated prescription class for use in randomization. The designated enrollment investigator will send the surgeon a staff message in EPIC to document that number for reference on the day of surgery.

Patients who agree to participate in the study will sign the consent form. The designated enrollment investigator will keep track of all patients who are consented for surgery but do not enroll in the study, collecting only the number of such patients and their reason for not entering the study (patient declines or which eligibility criterion is not met). No identifying data or other demographic data will be collected from patients who do not consent to enter the study. This information will be recorded in REDCap.

2. Randomization - < 1 minute

They will then be randomized to a study group using a REDCap stratified randomization protocol.

Randomization will be stratified by anticipated post-operative prescription (none, tramadol, 10 narcotic pills, 20 narcotic pills, 30 narcotic pills, >30 narcotic pills). Other factors that will be controlled for through randomization include:

1)

The surgeon and other treating providers will be blinded as to the randomization of the patient. In some cases, the patient may initiate a discussion with the surgeon which necessarily reveals the randomization – this is necessary to avoid interference with physician-patient communication (avoiding negatively impacting patient care) and will be considered acceptable for this study.

3. Data collection – enrollment phase – 10 minutes

An enrollment form is completed by the designated enrollment investigator based on patient interview and/or chart review at the time of enrollment.

At the pre-operative visit prior to video viewing, patients will complete, using REDCap online with the assistance of an investigator, the following:

- I. Quality of Recovery 15 (2.5 minutes)
- II. PROMIS short forms in the following domains: (approximately 6 minutes)
  - a. Physical Health – Gastrointestinal - Belly Pain 5a
  - b. Physical Health – Gastrointestinal – Nausea and Vomiting 4a
  - c. Mental Health – Cognitive Function 4a
  - d. Sleep Disturbance 4a
  - e. Pain Intensity 3a
  - f. Pain Interference 4a
- 4. Educational Intervention (experimental): (6-12 minute video, depending on randomization)
  - 1) Pain Management Education (Intervention)
    - a. A series of two 6-minute videos. The first video, Managing Pain after Outpatient Surgery, Part 1, discusses a tiered approach to pain management, including rest, ice, elevation, distraction, and medication. Three classes of pain medication commonly used after surgery, including nonsteroidal anti-inflammatories, acetaminophen, and opioids, are discussed, including the role of each medication and the risks and side effects. Naloxone, an antidote to opioid medication for emergency use, is introduced. The second video, Managing Pain after Outpatient Orthopedic Surgery, Part 2, instructs the patient on how to make a Pain Plan with regard to post-operative pain medication, including the use of over the counter pain medications and a medication diary. (12 minutes)
    - b. Recovery Medication Diary (1-7 minutes, daily, for 7 days)
  - 2) Wound Care Education (Control)
    - a. A single video, Caring for Your Closed Wound, discusses the types of sutures that are used to close surgical wounds, the specifics of wound care and dressing changes, swelling management, restriction of physical activity, scarring of the surgical site and

methods to reduce scarring, and guidance on when to call their physician if they suspect something to be wrong following their procedure. (6 minutes)

Patients are encouraged to view the video(s) in the examining room of the clinic before departure on a tablet device. Patients who elect to watch the video will be offered a small bottle of water, due to the extended visit and as a “fidget” to aid in attention. The videos will also be “assigned” to the patient in MyChart through the GetWellNetwork, and also available for viewing online on the Carilion channel on YouTube.

5. Patient packet dissemination (< 1 minute)

All patients in the study will receive an enrollment package with includes a copy of the consent form, video web address, and Patient Education Diary (experimental or placebo version). Patients in the Pain Control Video group will also receive a Recovery Diary corresponding to the video.

6. Data Collection (1-7 minutes daily for 7 days)

Patients are invited to view the video on the GetWellNetwork through MyChart and on YouTube. Viewing will be tracked by patient report, and by tracking views on the GetWellNetwork. (Viewing by patient report will be used in statistical analysis, comparison to GetWellNetwork data will be exploratory.)

Participants in both arms will complete a Patient Education Study Diary daily for 7 days following their surgery. Patients in the control group (wound care) will also record all pain medications used each day along with any side effects of the medications. Participants in the intervention (pain management) group will record their pain medication use in the additional Recovery Medication Diary provided.

Patients will receive a phone call from either an investigator or the study coordinator on Day 1-3 and Day 5-7 to remind them to complete their diaries and to answer any questions the patient may have (see attached script).

Patients will return their diaries at their first post-operative visit. If they do not bring the diaries to the post-operative visit, they will be given a self-addressed, stamped envelope to facilitate return. Patients will be contacted by phone (with permission) <10 days and 14-21 days following surgery and again 21-28 days after surgery if they have not returned their study materials as a reminder.

The Follow-up Questionnaire will be completed at the 1st post-operative visit, or by phone within 7-10 days of that appointment. The patient will be contacted again by phone and/or mail 1 year after surgery

(12-14 months) using the contact information available in EPIC to determine the self-reported prevalence of chronic pain and pain medication use:

1. Do you have pain on a daily or weekly basis?
2. In the past year, have you taken prescription opioid (or narcotic) pain medication most days or most weeks?
3. In the past year, have you used pain medications (prescription or over the counter) most days or most weeks? (list medications used on a daily or weekly basis for pain)

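### Item 20 lists randomisation before the investigator-assisted baseline QoR-15 and PROMIS forms, and nothing ensures that these baselines are recorded without knowledge of the arm.

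*Protocol*

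**What the plan says.** The heading of item 20 (Section III, Methodology) carries an instruction on order: "Please describe activities/procedures in a step-by-step chronological order". The numbered steps that answer it are:

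- **Step 1**, recruitment and consent. Here "The surgeon will inform the designated enrollment investigator (verbally) of the anticipated prescription class for use in randomization".
- **Step 2**, randomisation: "They will then be randomized to a study group using a REDCap stratified randomization protocol". On blinding it states: "The surgeon and other treating providers will be blinded as to the randomization of the patient".
- **Step 3**, enrolment-phase data collection: the enrolment form, then the QoR-15 and six PROMIS short forms. For the questionnaires, "At the pre-operative visit prior to video viewing, patients will complete, using REDCap online with the assistance of an investigator, the following".
- **Step 4**, the videos, which differ by arm.
- **Step 5**, the take-home packet, in which the diary version differs by arm.

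Item 17 makes the QoR-15 on post-operative day (POD) 2 the primary outcome, so the instrument recorded at step 3 is also the primary instrument. Item 22 describes a mixed model ANOVA that takes in all the data, and does not state the role of the baseline scores.

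**The concern.** The QoR-15 and the PROMIS forms are subjective self-reports, here completed with staff assistance. If the patient or the assisting investigator already knows the arm, the answers can shift with it. Someone just told that they will receive pain education, for example, may rate pain items differently from someone told that they will receive wound education. The score is then no longer a true baseline.

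The requirement that the forms come before the video keeps the content of the intervention out of the baseline. It does not keep out knowledge of the allocation. If such a baseline is used as a repeated measure, a change reference or a covariate, the shift passes into the estimated effect, and no analysis that uses the baseline can separate the two.

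**Working it through.** **1. Order and masking, from the text**

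| Question | What item 20 provides |
|---|---|
| Is baseline placed before randomisation? | No. It is step 3 and randomisation is step 2. The only timing condition is relative to the video. |
| Who is blinded? | The surgeon and other treating providers. |
| Is the enrolment investigator blinded? | Not stated. Step 1 says this person is not the treating physician, and receives the prescription class needed to randomise. |
| Is the investigator who assists with the forms blinded? | Not stated. |
| Is the patient kept unaware until the forms are saved? | Not stated. |
| When do arm-specific materials appear? | Steps 4 and 5, after the forms. |

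No other section of the protocol places the baselines before allocation or conceals the arm while they are recorded.

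**2. The plan's own sample size**

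Inputs from item 22 (power calculation): difference 8 points, SD 25, alpha 0.05 (taken as two-sided), power 0.80.

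- n per group = 2 × (1.960 + 0.842)² × 25² / 8² = 153.3, rounded up to 154. This matches the protocol.
- With 20% attrition: 154 / 0.80 = 192.5, rounded up to 193. This also matches.

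The formula compares one score between two groups and has no baseline or correlation term. For that comparison the bias from a shifted baseline is 0.

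**3. If the baseline is used**

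Let b be the arm-related shift in reported baseline QoR-15 (difference between arms) and r the correlation between baseline and POD 2, with equal SDs so that the regression slope equals r. Neither value is in the documents; both are assumptions. Sizes of bias:

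- POD 2 scores only: 0.
- Change score or group-by-time contrast: b, which is b/8 of the target difference.
- Baseline as covariate: about r × b, which is r × b/8 of the target difference.

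| Assumed b | Change score | Covariate, r = 0.3 | r = 0.5 | r = 0.7 |
|---|---|---|---|---|
| 0 points | 0% | 0% | 0% | 0% |
| 1 point | 12.5% | 3.75% | 6.25% | 8.75% |
| 2 points | 25% | 7.5% | 12.5% | 17.5% |

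The direction is opposite to the shift: a baseline raised in the intervention arm lowers the estimated benefit, and a lowered one inflates it.

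**4. Effect on the error rate, same assumptions**

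For the covariate-adjusted comparison with 154 per arm, SE = 25 × √(1 − r²) × √(2/154). With r = 0.5 this is 25 × 0.866 × 0.114 = 2.47 points. For b = 2 the bias is 1.0 point, or 0.41 SE, and the two-sided type I error is about 0.069 instead of 0.05. Across r = 0.3 to 0.7 it is 0.051 to 0.064 for b = 1 and 0.056 to 0.106 for b = 2.

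**The case against.** The strongest reply is that three unstated things must all happen for harm: the arm is disclosed before the forms, patients answer differently because of it, and the primary analysis uses the baseline. The protocol states none of them. Everything that would visibly show a patient the arm comes at steps 4 and 5. Both arms receive an educational video as an attention control, and the recruitment script speaks only of a video to help prepare for surgery. The consent form's wording is not available here, so what patients are told cannot be judged. The covariates named for analysis in item 20 are age, gender and factors related to the surgery and medication, not baseline QoR-15. Steps 2 and 3 may also be parts of one short session rather than a strict sequence.

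Most of this stands. It limits the likely size of the problem, and a POD 2 comparison without baseline remains available and unbiased. It does not remove the point. The order is the protocol's own answer to a request for chronology, the blinding statement leaves out the people who handle the forms, and a model taking in all the data leaves open the use of the one primary-instrument score measured before surgery. Falling back on POD 2 alone would avoid the bias only by giving up the baseline data collected.

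**Conclusion.** The point holds. As written, item 20 puts allocation before the baseline measurement of the primary instrument and does not ensure that this measurement is made without knowledge of the arm. That is the whole claim; disclosure itself is not shown.

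The bias is 0 for a comparison of POD 2 scores alone, b points for a change score or group-by-time contrast, and about r × b points with baseline as covariate. The size of b cannot be derived from the documents and may be zero, so the percentages above illustrate sensitivity and do not estimate a bias. The order of steps within the visit is trial conduct, which an analysis plan cannot repair afterwards. The change is advisable rather than essential, and is justified mainly because it is free.

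**What to change.** Swap steps 2 and 3 in item 20. After consent, complete and save the enrolment form, the baseline QoR-15 and the six PROMIS forms in REDCap, and open the randomisation only then. If the clinic already works this way, the text should say so.

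The swap has a second benefit. The abstract (item 15) says randomisation is also stratified by baseline pain medication use, which must be known before allocation, yet the enrolment form now appears after it. Completing that form first makes the factor available in time.

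The visit, forms, staff and sample size stay the same; only the order within the visit changes.
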